A structured medical record abstraction will be completed for each enrolled participant at the end of the study period to assess any clinical interactions (i.e. phone calls, clinic visits), healthcare utilization (i.e. ER visit or hospitalization for pain), or changes in pain/symptom management over the one-week study period and the week after (Appendix XB).

Cohort C: Clinician Lab UAT: Concurrent to Cohort A testing, we will conduct UAT of the web-based clinician portal of the application with relevant clinicians. With similar methodology to Lab UAT for Cohort A, up to 10 clinicians will "think aloud" while reviewing the clinician interfaces of STAMP (pre-populated with a set of test cases, not real patient data). Clinicians will be directly observed by the study team using a secure video-based screen-sharing platform (i.e. Zoom), or in person. Sessions will be recorded to assist with note taking. Following "think aloud" testing, clinicians will undergo a brief semi-structured debriefing interview and complete a validated usability survey (modified acceptability e-scale) (Appendix ZC). Clinicians will also complete a demographics survey (Appendix Y).

Findings will inform iterative revisions with repeat testing as needed. If common barriers are observed, the tool will be modified and repeat field UAT will be conducted until STAMP is found to be usable to most patients and providers.

Monitor subjects for safety or minimize risks:

The risks to participants in cohorts A, B, and C are minimal. The primary risk is loss of confidentiality/privacy. To monitor the risk of loss of confidentiality/privacy, the study team will ensure that the STAMP app is HIPPA compliant and meet the privacy and security standards set by DF/HCC. In addition, all collected study data will be maintained in a secure location and personal identifiers will be removed. As described above, UAT interviews will be recorded for the purpose of note-taking only, and will be destroyed as soon analysis concludes.

First, it is important to note that patient symptoms are imported into the clinician portal and severe symptoms are highlighted in red. This portal will be monitored once or twice per day by the study nurse. Therefore, patient symptoms will be reviewed more often by the team than with standard care practice and we anticipate they will receive earlier outreach for potentially worrisome symptoms.

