RA will ask the patient to complete a survey after signing consent [0-2 weeks], and at the end of study [4-8 weeks from intervention]. The survey can be completed remotely though a link to a Partners Healthcare compliant electronic survey system (e.g. REDCap), over the phone with the RA, over Zoom with the RA; in person with pen and paper or on a tablet. The Baseline survey will assess socio-demographics, barriers to pain management,¹³ pain severity,⁵¹ opioid use,¹⁹ symptoms,⁶² and quality of life,⁶³ with metrics shown in Table 9. Surveys will assess symptom

trajectory, medication use, and quality of life. End of study survey will largely replicate the baseline survey, additionally, patients will rate their satisfaction with STAMP using the 6-item Acceptability E-scale.⁵⁷ See Appendix AE for the Baseline survey items and Appendix AI for end-of-study survey items. Additionally, patients will be invited for a qualitative interview to ask a few open-ended questions about their experience to guide future refinements to the app (see Appendix AG).

Intervention

Cohort A: All patients on Cohort A will use the STAMP mobile phone App for 4 weeks. See below for a description of the intervention.

Intervention (Cohort A): After the patient completes the baseline survey, the RA will meet with the patient (in person or virtually), to assist in downloading the application onto participants' mobile device, register the patient to the app and help set up any preferences. The RA will then conduct a 15-minute tutorial on the STAMP app and its intended use [Appendix AC]. The RA will also input the patient's pain medications and laxatives from Epic, reconciling this list with the patient, and with the patient's nurse navigator if there are any discrepancies. During the trial, there is also a function in the app that allows participants to notify the research team if a medication needs to be changed and reflected in the app.

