- Acceptability: summary statistics will characterize acceptability ratings (e.g. mean and standard deviation), using #7 from our modified acceptability scale as our primary acceptability measure (“how would you rate your overall satisfaction with My Pain Pal App?”, with response options ranging from 1-5). Summary statistics will also assess acceptability on domains of ease of use, understandability, enjoyability, time required for use, learning, helpfulness, and likely to recommend to another patient.
- Usability: summary statistics will characterize usability from the system usability scale
- Exploratory outcomes: we will examine the number of symptom alerts generated by STAMP, the proportion of alerts that result in clinical action (e.g. phone calls or clinic visits), and medication changes.

Exploratory analyses will evaluate patient's symptom trajectories using a marginal model with GEEs, and mixed-effects models with patient as the random and time as the fixed effect.⁶⁴

Analysis of activity 5 (qualitative patient interviews): Because interviews produce qualitative results, statistical analyses will not be employed as part of this study. Qualitative thematic analysis will use a grounded theoretical approach in which two or more investigators will code transcripts and assign labels using an open coding approach. Investigators will name concepts and revise coding until consensus is reached. Analyses will be conducted using NVIVO analytic software, which the study PI will receive training in as part of this project.

ENDPOINT: The study team will use the qualitative results to help develop a new pain mobile health app for cancer patients.

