Appendix AH: Activity 4 – Informed consent form (Cohort A)

Appendix AI: Activity 4 – Patient end-of-study survey (Cohort A)

Appendix AJ: Activity 4 – Clinician interview guide (Cohorts B and C)

Appendix AK: Activity 4 – Clinician end-of-study survey (Cohorts B and C)

Appendix AL: Activity 4 – Patient recruitment script (Cohort A)

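### Does calling the end-of-study scale 6-item, when the primary acceptability rating is its item 7, leave the pilot's primary measure undefined?

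*Combined protocol and SAP*

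**What the plan says.** Section 10.0 makes feasibility and acceptability the primary outcomes of the pilot (Activity 4). Acceptability is to be summarised, for example by mean and standard deviation, "using #7 from our modified acceptability scale as our primary acceptability measure". The section prints the item, an overall-satisfaction question that names the app, with answers from 1 to 5. It adds summaries for "ease of use, understandability, enjoyability, time required for use, learning, helpfulness, and likely to recommend to another patient".

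Section 5.4, under the baseline survey for Cohort A, says that at the end of study "patients will rate their satisfaction with STAMP using the 6-item Acceptability E-scale", and sends the reader to "Appendix AI for end-of-study survey items". The measures table later in section 5.4 lists satisfaction as a novel metric, collected only at the second time point. Section 5.3 has Activity 3 clinicians "complete a validated usability survey (modified acceptability e-scale)". Section 33.0 lists Appendix AI as the "Patient end-of-study survey (Cohort A)".

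On payment, section 5.4 gives pilot patients USD 20 once consent is signed and USD 30 for the baseline survey, and states the total as USD 50. Section 28.0 gives each of the 20 pilot participants a USD 50 gift card when the study ends.

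**The concern.** The satisfaction rating is a primary outcome and is collected once. If the survey given to patients were an unmodified 6-item scale, the item that section 10.0 relies on might not be on it, and no later survey is scheduled to recover it. A reader of the results would also want to know whether the rating comes from the validated scale that section 5.4 cites or from an altered one.

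The payment mismatch seems to touch the same survey. Section 5.4 sets up the app only later: "After the patient completes the baseline survey, the RA will meet with the patient". The survey is then due "and at the end of study [4-8 weeks from intervention]". On the section 5.4 schedule the whole sum has been earned before app use starts. On the section 28.0 schedule all of it comes at the end. Completion of each assessment is one of the feasibility measures, so the timing of payment could matter for how many patients return the final survey.

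**Working it through.** No sample size, power or error rate is involved. The check is a count of items, a sum of payments and a comparison of sections.

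**Items**

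- Section 5.4 states 6 items, numbered 1 to 6.
- Section 10.0 uses item 7, so its scale has at least 7 items. Minimum gap: 7 − 6 = 1.
- Section 10.0 names 1 overall rating and 7 further domains: 1 + 7 = 8 constructs. Eight items follow only if each construct has exactly one item, which the documents do not say. Nor do they show that a 6-item form is the one patients receive. A count of domains left without an item therefore cannot be established.

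**What an analyst needs for the primary summary**

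| Element | Where it is given |
|---|---|
| Question wording | Section 10.0, printed in full |
| Response range, 1 to 5 | Section 10.0 |
| Statistic (mean, SD) | Section 10.0 |
| Time point (second only) | Measures table, section 5.4 |
| Patients (up to 20, single arm) | Section 5.4 |

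The mean is the sum of the ratings divided by the number answering. The item's position on the form does not enter that formula. With the question printed, an analyst finds the right column whether it is numbered 6, 7 or 8.

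**Which description looks out of date**

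- Section 10.0 calls the scale modified and prints a question that names this app.
- The measures table calls satisfaction a novel metric, which fits a modified scale better than a published one.
- The narrative in section 5.4 cites a barriers questionnaire (reference 13) and ESAS (reference 62). The measures table has no row for either and lists PRO-CTCAE instead.
- The table attaches the reference for the 6-item scale (57) to the row on use of STAMP, not to satisfaction.

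The narrative thus differs from the table in several places, and the 6-item label is probably one more leftover. This is an inference from the pattern; the documents do not state it.

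**Payment**

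- Section 5.4: 20 + 30 = 50, matching its stated total and the amount in section 28.0. Difference in total: 50 − 50 = USD 0.
- Still to be earned once app use begins: 50 − 50 = USD 0 under section 5.4, USD 50 under section 28.0.
- Treating the two as the same USD 50 is an inference from the same patients and the same amount. Nothing in the documents states USD 100.
- The documents give no figure linking payment timing to survey return, so no effect on completion or on the mean rating can be calculated.

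**The case for a change.** The strongest case for acting is that a procedures section should not describe a form that cannot contain the primary item as numbered. The rating has one collection point, and correcting the wording costs almost nothing. A benign explanation accounts for the mismatch but does not remove it from the text. The modified scale in section 5.3 is also for clinicians, so it does not settle what pilot patients receive. On payment, the difference is concrete for some patients: one withdrawn under section 15.0 for not completing the baseline survey would have USD 20 under section 5.4, while section 28.0 provides nothing before the study concludes.

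Part of this stands. The two labels disagree, the two payment schedules disagree, and patients should be told one schedule. What does not follow is a weakness in the design or analysis. The text sends the reader to Appendix AI for the survey items, and the consent form is listed separately as Appendix AH. Neither was available here, and that is no fault of the plan. Holding back part of the payment for the final survey would be a trade-off: it might help the final survey and might hurt baseline completion, and the documents give no figure for either. Section 10.0 already reports completion of each assessment, so a low return at the end would be visible.

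**Conclusion.** No change to the plan follows. The item mismatch is a clerical slip in one descriptive sentence, at least 1 item in size (7 against 6), and it concerns an outcome that section 10.0 fixes by wording, range and statistic. The payment mismatch is administrative: the same USD 50 with two timings. It belongs with the consent documents, not with the endpoints. The acceptability outcome is descriptive, with no threshold or test, so neither point alters a stated decision, an analysis or any result that can be computed.

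This rests on two assumptions: that Appendix AI carries the overall-satisfaction item as printed in section 10.0, and that both payment statements describe one USD 50. The mismatch between sections is certain. That a stale label explains it is likely but unproven. If Appendix AI proved to lack the item, the first point would become substantive, but nothing in the documents indicates that it does.

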11.0 Procedures Involved*

The study design, study procedures and safety monitoring varies by activity. See section 5.0 for details.

12.0 Data and Specimen Banking*

This study does not involve any specimen collection/banking of any kind.

Personal health information will be collected as part of this study.

All data collected during this study will be stored and used for future research. Any personal identifiers will be removed so that the information cannot be linked back to a patient.

Investigators can request the data collected from this study for new research. Data may also be shared with outside non-profit academic investigators as well as with for-profit pharmaceutical investigators or commercial entities with whom Dana-Farber collaborates. Requests must be sent to the study chair ([name]) and must be approved by the Dana-Farber IRB as well as the NIH prior to sharing.

The consent form informs the participant that data collected for this study may be used in the future. By consenting, participants agree. Participants will not be asked to provide additional informed consent for the use of de-identified information in future research.

There is no scheduled date on which the information and data that is being used or shared for this research will be destroyed, because research is an ongoing process.

13.0 Data Management* and Confidentiality

DF/HCC uses a clinical trial management system (CTMS) called OnCore, which is managed by the Office of Data Quality (ODQ).

- Activity 1 involves focus groups and interviews and is considered exempt research. We will NOT be collecting identifiable information from these participants. Therefore, we will not be using OnCore for participant registration.

- Activity 2 is NHSR; registration in OnCore is not applicable.
- Activity 3 involves user acceptability testing through interviews and focus groups. Patient participants will sign consent and we will collect basic demographic information. Patient participants WILL be registered in OnCore. For clinician participants, we will collect age group, gender, race, and ethnicity. We will NOT collect each participant's initials and date of birth. We will enter summary/batch accrual information into Dana-Farber's CTMS OnCore for Activity 3. Individual registration is not feasible as OnCore mandates DOB.
- Activity 4 involves pilot testing. Patient participants will sign consent and we will collect basic demographic information. Patient participants WILL be registered in OnCore. For clinician participants, we will collect age group, gender, race, and ethnicity. We will NOT collect each participant's initials and date of birth. We will enter summary/batch accrual information into Dana-Farber's CTMS OnCore for Activity 3. Individual registration is not feasible as OnCore mandates DOB.
- Activity 5 involves qualitative patient interviews. Patient participants will sign consent and we will collect basic demographic information. Patient participants WILL be registered in OnCore.

Data security: PHI data will be collected using multiple applications: REDCap and the STAMP app.

REDCap: For this study, data will be collected using the Partners instance of REDCap (redcap.partners.org). In collaboration with the Harvard Catalyst | The Harvard Clinical and Translational Science Center, REDCap (Research Electronic Data Capture) is a free, secure, HIPAA compliant web-based application hosted by Partners HealthCare Research Computing, Enterprise Research Infrastructure & Services (ERIS). Vanderbilt University, with collaboration from a consortium of academic and non-profit institutional partners, develops this software application for electronic collection and management of research and clinical study data. Data collection is customized for each study or clinical trial by the research team with guidance from ERIS REDCap administrators. REDCap is built around HIPAA guidelines and is 21 CFR Part 11 capable.

STAMP App: The final application will be HIPPA compliant and compliant with DFCI security and privacy standards

To maximize data security, both REDCap and the STAMP App will employ:

User Privileges. To ensure that users have access only to data and information that they are supposed to have within the application, user privileges are utilized within the software. Each user has their own account, and their user account will only have access to information that they themselves have created or to which administrators have granted them access.

Password-protection & Authentication. Both systems are password protected and implement authentication to validate the identity of end-users that log in to the system.

Auto-logout setting will automatically log a user out of the system if they have not had any activity (e.g. typing, moving the mouse) on their current web page for the set amount of time. This prevents someone else from accessing their account and their data if they leave a workstation without properly logging out or closing their browser window.

Logging and Audit Trail. Both systems maintain built-in audit trails that log all user activity and all pages viewed by every user.

Study specific procedure to maximize data security:

Controlled access: The REDCap and STAMP app administrators will set up all user accounts so that each user only has access to their own relevant participant data.

Use of unique study ID numbers: REDCap automatically assigns unique study ID numbers to each new case.

Extensive training: All personnel involved in this study are required to complete and document completion of extensive protocol training. Furthermore, all research personnel are required to have valid certification of human subjects research training.

Quality control: The staff at Dana-Farber will be responsible for monitoring the data for completion, accuracy, and compliance.

14.0 Provisions to Monitor the Data to Ensure the Safety of Subjects*

This is a social behavioral research project, not a treatment protocol. The study involves questionnaire-based assessments and symptom reporting and monitoring. As such, the only adverse event that will be monitored and reported is psychological distress as determined by the treating oncologist. For any patient who exhibits severe distress as result of the study procedures, the study research assistant will notify the patients' oncologist and social worker for appropriate response, including possible mental health referral if necessary. Furthermore, participants will be reminded that participation is voluntary and can be stopped at any time for any reason. See the DSMP (appendix F) for more details.

15.0 Withdrawal of Subjects*

Subjects who do not complete the baseline assessment within 1 week of study enrollment will be withdrawn from the research study without their consent. These patients will be informed of their withdrawal from the study by study staff.

The overall DF/HCC study PI, [name], will make all decisions regarding early termination of the study. The study team will then notify all participants accordingly.

16.0 Risks to Subjects*

There are risks to taking part in any research study. The primary risk of this study is loss of privacy or confidentiality. The risk of loss of privacy or confidentiality by using the STAMP app or taking part in this study is minimal. The study team has taken many steps to prevent any loss of privacy or confidentiality, including training of all clinic and research staff in best practices, rules, and regulations surrounding privacy and confidentiality, collecting research data using unique study ID numbers instead of names or other identifying information, and use of data collection systems that meet the NIH's data security standards.

17.0 Potential Benefits to Subjects*

Using the STAMP app and taking part in this research study may or may not benefit participants. We hope that by using the STAMP app, patients are able to better manage their symptoms and the increased flow of information between a patient and their care team improves their experiences. We also hope the information learned from this research study will provide more information about how to best help patients, caregivers, and their care team work together during and between visits to achieve better symptom management in cancer patients.

18.0 Vulnerable Populations*

This research does not involve vulnerable populations of prisoners, children, cognitively impaired adults, or pregnant women. Prisoners, children, cognitively impaired adults, and pregnant women are excluded.

19.0 Community-Based Participatory Research*

Not applicable to this study.

20.0 Sharing of Results with Subjects*

Participants will be directed to clinicaltrials.gov for research study results.

21.0 Setting

This is a pilot study that will take place at Dana-Farber.

22.0 Resources Available

This study team will be taking place under the Population Sciences Division at Dana-Farber. The Population Sciences Division maintains its own server infrastructure and systems administration staff that provide data storage, data backup, and data security in support of large data analysis projects. The servers are configured as a virtual server pool with virtual server hosts connected to a centralized Storage Area Network (SAN) device. Server virtualization increases the efficiency and flexibility of the server pool while minimizing downtime and cost. The server pool currently has 20 processor cores and a data storage capacity of 9 terabytes. This server infrastructure has a dedicated Systems Administrator to optimize performance, maintain security patches, perform

backups, and execute other related tasks. Researchers in the Division have access to additional resources through the Research Computing group. Research Computing provides a variety of services including file server space, backup services, website hosting, and support of some workstation computers.

Additionally, the research team is well-qualified to perform their duties. [name] has extensive experience in conducting research studies in cancer disparities, health services, and education. She has deep knowledge of the clinical and research environments and the patient population and culture at DFCI.

